
### 15.4 Analysis of Secondary Endpoints

To evaluate the *preliminary efficacy* of lorcaserin versus placebo to reduce cocaine use and HIV-related sexual risk behaviors among MSM with cocaine use disorders, as determined by the proportion of cocaine-positivity from twice weekly urine samples and self-reported sexual behaviors. Minimum detectable effects (MDE) of the intervention on cocaine use outcomes will be substantial, as is typical of a pilot study. In our prior trial for MSM actively using stimulants, the within-subject correlation of the repeated measures for urine positivity was 0.45, the urine positivity in the control group was 55%, and the retention was 93% at the end of the study. On this basis, we conservatively estimate that the sample will provide 80% power to detect reductions of 29 percentage points in the rate of cocaine urine positivity. In preparation for a larger trial, we will conduct exploratory assessments using GEE Poisson models to assess treatment effects on cocaine urine positivity. In sensitivity analyses, we will also evaluate between-group differences on changes in: 1) any cocaine positive samples, defined as having a positive urine or sweat patch sample, over follow-up; 2) any cocaine positive samples or self-report of cocaine use in text messages; and 3) cocaine positivity from sweat samples only. Concordance of the urine testing, sweat testing, and self-reported measures will be examined using weighted Kappa and correlations. To evaluate treatment effects on cocaine-associated sexual risk behaviors, GEE Poisson, binomial, and negative binomial models will be used to assess treatment effects on HIV sexual risk behaviors including high-risk sexual behaviors while under the influence of cocaine. **Findings from these analyses will be used to determine whether a linearly increasing or constant treatment effect best describes outcome patterns.**

Safety and tolerability data will be summarized by treatment group.

Adverse event rates will be coded by body system and MedDra classification term. Adverse events will be tabulated by treatment group and will include the number of patients for whom the event occurred, the rate of occurrence, and the severity and relationship to study drug.

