## 5. CRITERIA FOR EVALUATION

### 5.1 Primary Efficacy Endpoint

For the primary efficacy endpoint, we conservatively estimate that the sample will provide 80% power to detect reductions of 29 percentage points in the rate of cocaine urine positivity. The time course for which this endpoint will be assessed will be from baseline to 12 week end of treatment. We will also evaluate between-group differences on changes in: 1) any cocaine positive samples, defined as having a positive urine or sweat patch sample, over follow-up; 2) any cocaine positive samples or self-report of cocaine use in text messages; and 3) cocaine positivity from sweat samples only.

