### 6.2 Inclusion Criteria

- 1) Male gender;
- 2) self-reported anal intercourse with men in the prior six months while under the influence of cocaine;
- 3) cocaine use disorder by DSM-V SCID criteria;
- 4) current cocaine use confirmed by urinalysis and cocaine use at least 1 day in the past 30 days;
- 5) HIV-negative by rapid test or HIV-positive with medical record of HIV infection;
- 6) no current acute illnesses requiring prolonged medical care;
- 7) no chronic illnesses that are likely to progress clinically during trial;
- 8) able and willing to provide informed consent and adhere to visit schedule;
- 9) age 18–65 years;
- 10) Baseline CBC, total protein, albumin, glucose, alkaline phosphatase, creatinine, BUN, and electrolytes without clinically significant abnormalities as determined by study clinician in conjunction with symptoms, physical exam, and medical history.
- 11) Written informed consent (and assent when applicable) obtained from subject or subject's legal representative and ability for subject to comply with the requirements of the study.

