**10. EVALUATIONS BY VISIT****10.1 VISIT 1 (SCREENING VISIT—WEEK 1)**

Review the study with the subject (subject's legal representative) and obtain written informed consent and HIPAA authorization and assent, if appropriate.

Assign the subject a unique screening number.

Record demographics data.

Record medical history, including a history of mental health, sexual behaviors and substance use, diagnosis date, and prior cocaine treatments.

Record concomitant medications.

Perform a complete physical examination.

Collect urine sample for cocaine use and other substances test. If capable of becoming pregnant then a pregnancy test. Record results.

If urine is not positive for cocaine metabolites then place a sweat patch on participant.

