### **10.2 Visit 2 (Screening Visit – week 2)**

Perform and record vital signs (including weight and height for calculating BMI)

Perform and record results of blood pressure testing.

Perform and record results of ECG

Collect blood for clinical laboratory tests (chemistry, hematology, HIV test, pooled viral load test. If HIV positive, a CD4 test).

Collect and record contact information

Collect urine sample for cocaine use and other substances test. If capable of becoming pregnant then a pregnancy test. Record results.

If urine is not positive for cocaine metabolites then place a sweat patch on participant.

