### 15.2 Demographic and Baseline Characteristics

The following demographic variables at screening will be summarized by treatment group: race, gender, age, educational attainment, employed, and HIV positivity.

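### Optional precision gain: the Section 15.4 cocaine-positivity models name no baseline cocaine-use covariate, although urine is already tested at both screening visits and at enrollment

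*Combined protocol and SAP*

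**What the plan says.** Section 15.4 states that "we will conduct exploratory assessments using GEE Poisson models to assess treatment effects on cocaine urine positivity". It names no covariate for these models. The same section reports from a prior trial that "the within-subject correlation of the repeated measures for urine positivity was 0.45", with 55% positivity in controls and 93% retention, and gives 80% power for a 29-point reduction. For three sensitivity outcomes (urine or patch, those plus text reports, and sweat only), it says "we will also evaluate between-group differences on changes in".

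Section 5.1 says of the urine endpoint: "The time course for which this endpoint will be assessed will be from baseline to 12 week end of treatment". It does not say how a baseline value enters a model.

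The Section 15.2 baseline summary covers "race, gender, age, educational attainment, employed, and HIV positivity", with no measure of cocaine use.

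Pre-treatment use is nevertheless measured. Inclusion criterion 4 requires "current cocaine use confirmed by urinalysis and cocaine use at least 1 day in the past 30 days". Section 10.1 schedules a cocaine urine test at the first screening visit and adds "If urine is not positive for cocaine metabolites then place a sweat patch on participant". Section 10.2 repeats the test at the second visit ("Collect urine sample for cocaine use and other substances test"), and Section 10.3 lists another at enrollment. Appendix 1 marks urine testing in both columns. Section 15 promises a detailed SAP before the final analysis.

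**The concern.** In a small trial with a repeated binary outcome, a participant's use before treatment is often the best available predictor of use afterwards. Adjusting for it removes chance imbalance and unexplained between-person variation. Here the placebo arm has 15 people, so the estimate will be imprecise, and Section 2.1 wants the pilot to inform the size of a larger trial. A covariate already being collected may be left unused. If it is chosen only after unblinding, the choice could be influenced by the result. What is at stake is precision, not validity.

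**Working it through.** **Inputs from the plan.** Arms of 30 and 15 (Section 4.1). Control positivity 55%, reduction 29 points (so 26% on active), within-subject correlation 0.45, retention 93% (Section 15.4). The number of samples per person, m, is 24 if urine is twice weekly (Section 15.4) or 12 if weekly (Section 9.1). Two-sided alpha of 0.05 is my assumption.

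**Step 1: the plan's own figure.** Variance factor d = (1 + (m − 1) × 0.45)/m, which is 0.473 for m = 24 and 0.496 for m = 12. SE = sqrt(d × [0.55 × 0.45/n0 + 0.26 × 0.74/n1]).

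- m = 24, n = 30 and 15: SE = sqrt(0.4729 × 0.02291) = 0.104. Power = Φ(0.29/0.104 − 1.96), about 80%. The stated 80% is therefore reproduced without any adjustment.
- m = 12, 93% retained (27.9 and 13.95): SE = sqrt(0.4958 × 0.02464) = 0.1105, power about 75%.

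**Step 2: unadjusted half-width (1.96 × SE).** 20.4 (m = 24) to 20.9 (m = 12) points at full numbers; 21.2 to 21.7 with 93% retained; 22.0 to 22.5 if both arms are at 55%.

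**Step 3: how well pre-treatment urine predicts follow-up.** If the 0.45 correlation extended unchanged to three pre-treatment urines in unselected people, r between their mean and the mean of 12 follow-up samples would be 0.45/sqrt((1.9/3) × 0.496) = 0.80. Criterion 4 rules that figure out, because it selects people who test positive and so narrows the spread. I used a logistic-normal model calibrated to 55% and 0.45 (random-effect SD 2.34). People were selected on at least one positive screening urine, and pre-treatment positivity before selection was set at 55, 74 or 87%. Persistence is the assumed correlation between a person's underlying propensity before and after treatment starts.

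| Assumed persistence | r, three-urine fraction with follow-up |
|---|---|
| Full (1.0) | 0.65, 0.63, 0.53 |
| Partial (0.7) | 0.38, 0.38, 0.35 |
| Weak (0.4) | about 0.20 |

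If both screening urines must be positive, r at 55% positivity falls to 0.42, 0.22 and 0.11. A separate latent-normal model with full persistence gave R² of 0.42 to 0.46 for the three-urine mean (r about 0.65 to 0.68), against 0.27 to 0.29 for the enrollment urine alone. A single yes/no result is therefore the weaker covariate.

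**Step 4: what a given r buys.** Poisson GEE, 28 against 14 people, 12 samples, Mancl-DeRouen variance, 10,000 runs per setting:

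| r | Power, unadjusted to adjusted (%) | Half-width, points |
|---|---|---|
| 0.23 | 74.6 to 74.0 | 21.3 to 21.4 |
| 0.33 | 75.6 to 77.1 | 21.6 to 21.3 |
| 0.54 | 75.1 to 83.0 | 21.7 to 20.4 |
| 0.65 | 75.0 to 87.7 | 21.2 to 19.0 |

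The half-widths change by about +0.5, −1, −6 and −10%. The shortcut 1 − sqrt(1 − r²) would promise narrowing of 2.7, 5.6, 16 and 24%, so it overstates the gain.

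Combining steps 3 and 4: weak persistence gains nothing. For partial persistence, interpolating between r = 0.33 (1.5 points) and 0.54 (7.9 points) gives 1.5 + (0.02/0.21) × 6.4 = 2.1 points at 0.35 and 1.5 + (0.05/0.21) × 6.4 = 3.0 points at 0.38. Full persistence gains about 8 to 13 points.

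**Step 5: test size.** In simulations under no effect, the adjusted test rejected 3.6 to 4.6% of the time with the small-sample correction and 5.4 to 6.7% without it. A smaller run without it, 1,000 repetitions with people selected on screening urine, gave 7.3%.

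**The case against.** The strongest reply is that this is a preference. The trial is a feasibility pilot, Section 15.4 calls these models exploratory and concedes that detectable effects are large, and the promised SAP is the usual place for covariates. All of that stands, and it sets the weight of the point.

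A second reply is that the text on the period from baseline, and on changes, may already mean a longitudinal model with baseline as one of the outcome times. That is possible, and the comparison in step 4 would then not describe the plan. But no section says how baseline enters the urine model, so the request to state it remains.

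A third reply is that the gain rests on assumptions. This is right. The 0.45 comes from a prior stimulant trial, and its extension to pre-treatment samples is not in the documents. Nor do they say whether one positive screening urine is enough for entry. Selection also raises expected follow-up positivity (to about 71% in the latent-normal model with full persistence), so reading power from step 4, which holds control positivity at 55%, is approximate. Recalibrating so that selected participants average about 55% returns r to about 0.72, so the upper end of the range is not firm either. The step 4 simulation also starts from weekly sampling, the lower-power version. The weekly and twice-weekly statements need reconciling in their own right.

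A reader might infer that the unadjusted analysis is biased, or that the 80% power claim fails without adjustment. Neither follows: randomisation protects the unadjusted comparison, and step 1 reproduces the 80%. A reader might also apply the 0.45 directly and expect adjusted power above 90%. That ignores the selection imposed by criterion 4 and assumes that use persists fully.

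**Conclusion.** The observation holds as an optional improvement. No baseline cocaine-use covariate is named, and suitable data are already scheduled. The unadjusted analysis is valid, with a half-width of about 20 to 22 points. Adjustment could add anything from nothing to about 8 to 13 points of power, depending mainly on persistence of use, which the documents do not give. The lower end is as plausible as the upper. Confidence is high on the facts and moderate on the size.

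**What to change.** In Section 15.4 or the promised SAP, before unblinding:

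1. Prespecify one graded baseline-use covariate in the urine, patch and composite positivity models. Use days of cocaine use in the past 30 if a count is recorded, and name the source. TLFB is mentioned in Section 15.3 but appears in no visit list; the enrollment ACASI in Section 10.3 is another candidate.
2. If no count exists, use the proportion of the Screening 1, Screening 2 and Enrollment urines that are positive. Count the enrollment sample only if it is taken before the first dose. Section 10.3 lists randomisation ahead of that sample and does not give the time of the first dose.
3. Report the unadjusted estimate alongside.
4. Use a small-sample sandwich variance such as Mancl-DeRouen. This is advisable with or without the covariate.

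Two side points can go in the same edit. Add baseline cocaine use to the Section 15.2 summary. State whether the changes in the sensitivity outcomes are measured from baseline; sweat-only positivity generally has no pre-treatment value, because Section 9.1 first affixes patches on all participants at the baseline visit.

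The cost is SAP wording only, since the urine samples are already scheduled. The downside is one extra parameter per model in 45 people, with no gain if baseline use predicts follow-up only weakly (r of about 0.25 or less).

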### 15.5 Interim Analysis

No planned interim analysis.

### 15.6 Sample Size and Randomization

## 16 DATA COLLECTION, RETENTION AND MONITORING

### 16.1 Data Collection Instruments

The Investigator will prepare and maintain adequate and accurate source documents designed to record all observations and other pertinent data for each subject treated with the study drug.

Study personnel at each site will enter data from source documents corresponding to a subject's visit into the protocol-specific paper CRF when the information corresponding to that visit is available. Staff will upload data to the eCRF. Subjects will not be identified by name in the study database or on any study documents to be collected, but will be identified by subject number and date.

*For eCRFs:* If a correction is required for an eCRF, the time and date stamps track the person entering or updating eCRF data and creates an electronic audit trail. *For paper CRFs:* If a correction is made on a CRF, the study staff member will line through the incorrect data, write in the correct data and initial and date the change.

The Investigator is responsible for all information collected on subjects enrolled in this study. All data collected during the course of this study must be reviewed and verified for completeness and accuracy by the Investigator. A copy of the CRF will remain at the Investigator's site at the completion of the study.

## **16.2 Data Management Procedures**

The data will be entered into a validated database. The Data Management group will be responsible for data processing, in accordance with procedural documentation. Database lock will occur once quality assurance procedures have been completed.

All procedures for the handling and analysis of data will be conducted using good computing practices meeting FDA guidelines for the handling and analysis of data for clinical trials.

## **16.3 Data Quality Control and Reporting**

After data have been entered into the study database, a system of computerized data validation checks will be implemented and applied to the database on a regular basis. *For paper studies:* Query reports (Data Clarification Requests) pertaining to data omissions and discrepancies will be forwarded to the Investigators and study monitors for resolution. The study database will be updated in accordance with the resolved queries. All changes to the study database will be documented.

## **16.4 Archival of Data**

The database is safeguarded against unauthorized access by established security procedures; appropriate backup copies of the database and related software files will be maintained. Databases are backed up by the database administrator in conjunction with any updates or changes to the database.

At critical junctures of the protocol (e.g., production of interim reports and final reports), data for analysis is locked and cleaned per established procedures.

## **16.5 Availability and Retention of Investigational Records**

The Investigator must make study data accessible to the monitor, other authorized representatives of the Sponsor (or designee), IRB, and Regulatory Agency (e.g., FDA) inspectors upon request. A file for each subject must be maintained that includes the signed Informed Consent, HIPAA Authorization and Assent Form and copies of all source documentation related to that subject. The Investigator must ensure the reliability and availability of source documents from which the information on the CRF was derived.

All study documents (patient files, signed informed consent forms, copies of CRFs, Study File Notebook, etc.) must be kept secured for a period of two years following marketing of the investigational product or for two years after centers have been notified that the IND has been discontinued. There may be other circumstances for which the Sponsor is required to maintain

study records and, therefore, the Sponsor should be contacted prior to removing study records for any reason.

### **16.6 Monitoring**

Monitoring visits will be conducted by representatives of the Sponsor according to the U.S. CFR Title 21 Parts 50, 56, and 312 and ICH Guidelines for GCP (E6). By signing this protocol, the Investigator grants permission to the Sponsor (or designee), and appropriate regulatory authorities to conduct on-site monitoring and/or auditing of all appropriate study documentation.

### **16.7 Subject Confidentiality**

In order to maintain subject confidentiality, only a subject number and subject initials will identify all study subjects on CRFs and other documentation submitted to the Sponsor. Additional subject confidentiality issues (if applicable) are covered in the Clinical Study Agreement.

## **17 ADMINISTRATIVE, ETHICAL, REGULATORY CONSIDERATIONS**

The study will be conducted according to the Declaration of Helsinki, Protection of Human Volunteers (21 CFR 50), Institutional Review Boards (21 CFR 56), and Obligations of Clinical Investigators (21 CFR 312).

To maintain confidentiality, all laboratory specimens, evaluation forms, reports and other records will be identified by a coded number and initials only. All study records will be kept in a locked file cabinet and code sheets linking a patient's name to a patient identification number will be stored separately in another locked file cabinet. Clinical information will not be released without written permission of the subject, except as necessary for monitoring by the FDA. The Investigator must also comply with all applicable privacy regulations (e.g., Health Insurance Portability and Accountability Act of 1996, EU Data Protection Directive 95/46/EC).

### **17.1 Protocol Amendments**

Any amendment to the protocol will be written by the Principal Investigator. Protocol amendments cannot be implemented without prior written IRB approval except as necessary to eliminate immediate safety hazards to patients. A protocol amendment intended to eliminate an apparent immediate hazard to patients may be implemented immediately, provided the IRBs are notified within five working days.

### **17.2 Institutional Review Boards**

The protocol and consent form will be reviewed and approved by the IRB of each participating center prior to study initiation. Serious adverse experiences regardless of causality will be reported to the IRB/IEC in accordance with the standard operating procedures and policies of the IRB/IEC, and the Investigator will keep the IRB/IEC informed as to the progress of the study. The Investigator will obtain assurance of IRB/IEC compliance with regulations.

Any documents that the IRB/IEC may need to fulfill its responsibilities (such as protocol, protocol amendments, Investigator's Brochure, consent forms, information concerning patient recruitment, payment or compensation procedures, or other pertinent information) will be submitted to the IRB/IEC. The IRB/IECs written unconditional approval of the study protocol

and the informed consent form will be in the possession of the Investigator before the study is initiated. The IRB/IECs unconditional approval statement will be transmitted by the Investigator to prior to the shipment of study supplies to the site. This approval must refer to the study by exact protocol title and number and should identify the documents reviewed and the date of review.

Protocol and/or informed consent modifications or changes may not be initiated without prior written IRB approval except when necessary to eliminate immediate hazards to the patients or when the change(s) involves only logistical or administrative aspects of the study. Such modifications will be submitted to the IRB and written verification that the modification was submitted and subsequently approved should be obtained.

The IRB must be informed of revisions to other documents originally submitted for review; serious and/or unexpected adverse experiences occurring during the study in accordance with the standard operating procedures and policies of the IRB; new information that may affect adversely the safety of the patients of the conduct of the study; an annual update and/or request for re-approval; and when the study has been completed.

### **17.3 Informed Consent Form**

Informed consent will be obtained in accordance with the Declaration of Helsinki, ICH GCP, US Code of Federal Regulations for Protection of Human Subjects (21 CFR 50.25[a,b], CFR 50.27, and CFR Part 56, Subpart A), the Health Insurance Portability and Accountability Act (HIPAA, if applicable), and local regulations.

The Investigator will prepare the informed consent form, assent and HIPAA authorization and provide the documents to the Sponsor or designee for approval prior to submission to the IRB/IEC. The consent form generated by the Investigator must be acceptable to the Sponsor and be approved by the IRB. The written consent document will embody the elements of informed consent as described in the International Conference on Harmonisation and will also comply with local regulations. The Investigator will send an IRB-approved copy of the Informed Consent Form to the Sponsor (or designee) for the study file.

A properly executed, written, informed consent will be obtained from each subject prior to entering the subject into the trial. Information should be given in both oral and written form and subjects (or their legal representatives) must be given ample opportunity to inquire about details of the study. If appropriate and required by the local IRB, assent from the subject will also be obtained. If a subject is unable to sign the informed consent form (ICF) and the HIPAA authorization, a legal representative may sign for the subject. A copy of the signed consent form (and assent) will be given to the subject or legal representative of the subject and the original will be maintained with the subject's records.

